13.5 Correlative and companion substudy analyses

13.5.1 Correlative substudy analysis (A211401)

Salivary cotinine is an evidence-based biochemical method to confirm tobacco use that significantly increases the accurate identification of current smoking. Data demonstrate that 30-40% of cancer patients who smoke do not accurately report smoking status even using structured assessments (97-98). As a result, quantitative cotinine analyses (96) will be used to increase the accuracy of identifying current smoking, which will in parallel be used to evaluate changes in study outcomes using a more accurate methodology. For this study, a cutoff of 15 ng/mL will be used to define biochemically confirmed current smoking (>15) according to recommendations from the Society for Nicotine and Tobacco Research (95).

13.5.2 Pharmacogenetic companion substudy analysis (A211401-PP1)

For the correlative analysis, we will examine whether cigarette smokers undergoing surgery for cancer who have the high-risk variants of *CHRNA5-CHRNA3-CHRNA4* will have higher abstinence rates, as determined by the tobacco use assessment and cotinine levels, than those with the low-risk variants of *CHRNA5-CHRNA3-CHRNA4*. We will examine this genetic effect in the overall group and in each treatment arm. We will also examine whether

intervention effect varies with *CHRNA5-CHRNA3-CHRNA4* (i.e. a genotype X intervention interaction). A series of logistic regression models will be used to examine main effects of genotype and intervention before testing genotype x intervention interactions, with age, sex, and intervention arm as covariates. Similarly, we will examine whether smokers with *CYP2A6*-defined fast nicotine metabolism will have lower abstinence and higher withdrawal symptoms at 12 weeks after surgery and at 24 weeks after surgery (end of study), compared with smokers with slow metabolism. We will examine whether the effect of varenicline varies with participant's *CYP2A6*-defined nicotine metabolism status. Fisher exact tests will be used, supplemented by logistic regression models similar to what is described for the primary analysis. We will examine if these cessation-relevant genotypes (*CHRNA5-CHRNA3-CHRNA4*, *CYP2A6*) modify the effect of the intervention vs. control groups. These correlative analyses will not be adjusted for multiple comparisons, since the magnitude of the associations is of more interest than the statistical significance for whether or not there is any association.

13.6 Power/Sample Size

The primary statistical endpoint for this study is the incidence of surgical complications as described in Sections 13.1 and 13.3. Patients that have any of these individual morbidities will be considered to have a perioperative complication. Patients without any of these individual morbidities will be considered to not have a perioperative complication.

In a study of 635,265 non-cardiac surgical cases treated in 200 centers throughout the United States, the incidence rate of the perioperative complications listed above from the National Surgical Quality Improvement Program (NSQIP) data was in the range of 25–30%. They further found that smokers undergoing non-cardiac surgery had an estimated 40% increased odds of developing major morbidity and mortality within 30 days of surgery over never smokers, representing a modest difference of between 10%-12% in the actual percentage of patients with major morbidity.[90] One report focused on the limitations of NSQIP in identifying adverse events following major cancer surgery. NSQIP does not abstract the complications considered most important by many surgical subspecialists (e.g., anastomotic leak).[91] Therefore, the true impact of smoking on adverse surgical events may be greater in this trial.

For the purposes of this power calculation then, we will assume a 30% perioperative complication incidence rate in the control group.¹⁰⁴ The study design is a randomized clinical trial intended to estimate the incidence rate of perioperative complications in patients who are smoking at the time of enrollment. The primary statistical analysis will be a comparison of the perioperative complication incidence rates from the time of surgery to 24 weeks after surgery between the intervention and control groups. We will hence power the study to detect a 10% difference in perioperative complication rates between the intervention and control groups.

With a sample size of 626 patients (313 patients per arm), a Fisher exact test can detect a difference in the perioperative complication rate between the two treatment groups of 10% (20% versus 30% in the intervention arm and control arm, respectively) with 80% power using a Type I error rate of 5% and a two-sided alternative.

The prevalence of smoking among lung cancer surgical patients is roughly 42%.[91] We estimate that 90% of these patients will be motivated to quit and enroll on the study, given the relaxed eligibility requirements requiring only a desire to quit and teachable moment delivery by the surgeons. Hence we can expect to screen roughly three patients to enroll one. An adjustment is also needed for patients that enter the smoking cessation part of the study, but drop out before surgery. We expect that at most 20% of the patients entering the study will drop out after registering and before having surgery. To obtain a sample size of 626 smoking patients with a new diagnosis of lung cancer for which surgery is indicated, we will need to screen

approximately 1878 oncology patients undergoing surgery to enroll 783 smoking patients. Of these 783 patients, we expect 626 to undergo surgery. The study will remain open to accrual until 783 patients have been enrolled. If we take into consideration patient refusal, we would need to approach 2000 smoking oncology patients undergoing surgery to have 626 patients enroll in the study and undergo surgery.

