1.1.2. Benefits of Smoking Cessation in Cancer Patients

Quitting smoking has beneficial health effects regardless of patient age.[13] Individuals who stop smoking significantly decrease their risk of lung cancer compared to current smokers.[7] For patients diagnosed with cancer, smoking cessation can improve cancer

treatment tolerance and effectiveness,[14, 15] overall survival,[13] prevention of second primary malignancy,[8, 16] and QOL.[17] Multimodal cancer therapy most often includes surgical procedures. Minimizing postoperative complications in oncology patients undergoing surgical procedures is of paramount importance both for minimizing treatment-related morbidities and for allowing a patient to go on to other components of the multimodal therapy. A reduction in complications has been observed within 4 weeks of smoking cessation.[18] Smoking cessation is beneficial at any time point relative to lung cancer surgery, but “current” smoking status at the time of surgery has been associated with a poor postoperative QOL.[19] A recent meta-analysis of 6 studies addressing smoking and surgical complications found that stopping smoking can reduce the relative risk of postoperative complications by 41% (95% CI, 15% to 59%; $P = 0.01$); each week of cessation prior to surgery increased this effect by 19%.[20] In addition, stopping smoking prior to chemotherapy and radiation therapy reduces the total symptom burden (sum of 12 symptoms scored on an 11-point Likert scale) of cancer treatment during treatment (smokers vs. nonsmokers: 46.3 vs. 41.2; $P < 0.05$) and at 6 months after treatment (27.7 vs. 21.9; $P < 0.05$).[21] Fewer than 10% of smokers actively seek treatment for tobacco dependence. Over 80% of providers in oncology practices provide brief smoking cessation counseling, but fewer than 30% ask about smoking in subsequent visits.[22] Barriers to smoking cessation among oncology patients include provider lack of confidence and patient lack of motivation.[22] Adjunctive use of a self-help guide for stopping smoking has been associated with improved motivation and has been found to be a predictor of long-term smoking cessation in oncology patients.[23, 24] Thus, effective methods for smoking cessation exist, but they have not been tested in the setting of a multicenter clinical trial targeting cigarette-smoking oncology patients who are scheduled for surgery.

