1.3 Study Overview

This will be a randomized clinical trial. The primary goal is to assess the effect of smoking cessation treatment on surgical complications. We will also report the impact of alternative treatments on QOL and post-operative care. According to the US Guidelines[1], although counseling and medication are effective when used alone, the combination of both is more effective than either alone. Thus clinicians should encourage smokers who want to quit, to use both counseling and medication in trying to quit smoking (#7 of the 10 key guideline recommendations). In this study, 626 cancer surgery patients will be randomized 1:1 to a "protocolized" smoking cessation program (varenicline plus a brief no-smoking message from the surgical team and behavioral support provided by a telephone smoking quitline [NCI's [name]]), or to placebo plus a brief no-smoking message from the surgical team and behavioral support provided by the telephone smoking quitline). Surgery must occur after the target quit date (TQD) defined at baseline and can be performed no sooner than 10 days after randomization and no more than twelve weeks after randomization. The study will remain open to accrual until 626 patients have had surgery and are followed for 24 weeks after surgery for surgical complications. The primary outcome will be the rate of surgical complications, as identified from an investigation of the American College of Surgeons-National Surgical Quality Improvement Program (ACS-NSQIP). Secondary outcomes include QOL, post-operative care (length of hospital and high dependency unit stay), and rates of smoking abstinence. All study participants will have the option of enrolling in the correlative genetic study. This correlative study will look at important genetic variants in nicotinic receptor gene cluster (*CHRNA5-CHRNA3-CHRNA4*) and nicotine metabolism (*CYP2A6*) that have been shown to impact successful smoking abstinence. This will include a blood draw at baseline, and tobacco use outcome will be determined by salivary cotinine at baseline and every six weeks after surgery for 12 weeks, with a final measurement at 24 weeks.

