1.4 Feasibility, Accrual Time, and Study Duration

A survey of legacy ACOSOG thoracic surgeons and the Alliance Community Oncology Committee members has shown that the vast majority of sites that see these patients would be interested in accruing patients for this study. From accrual estimates provided by sites in this survey, we anticipate accruing 150 evaluable patients per year. In the opinion of these surgeons, this study is highly feasible to accrue quickly. We conducted a follow-up survey asking surgical practices to describe in detail the manner in which the workflow for the study would be carried out. This survey provides us with example templates to guide potential participating sites. Given these data and our past experience with accruing patients to smoking cessation studies, we anticipate that our accrual estimate is conservative. In previous NCCTG trials accrual rates of as high as 25 patients per week were achieved, albeit in mixed treatment practices. As already indicated, however, we have done multiple surveys of Alliance surgical practices who indicate strong support for the study, with specific accrual expectations and workflow details. Hence the sites are unusually well prepared and aware of the needs to accrue to this study and are eagerly awaiting the trial opening. That likelihood of rapid accrual, plus the involvement of surgeons in the prevention aim, is a major selling point for the trial. This study accrual will close when

626 study patients have undergone surgery; therefore, we anticipate patient accrual to be completed in approximately 4 years and 2 months.

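### The plan closes accrual at 626 operated in 1.3 and 1.4 but at 783 (or 700) enrolled in 13.6 and 13.7; two supporting figures in 13.6, 1878 screened and 10–12 points, also need correction or a source check

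*Combined protocol and SAP*

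**What the plan says.** **Closing rule.** Section 1.3: "The study will remain open to accrual until 626 patients have had surgery". Section 1.4 closes accrual when "626 study patients have undergone surgery; therefore, we anticipate patient accrual to be completed in approximately 4 years and 2 months". Section 13.6 instead keeps the study open until 783 are enrolled, and 13.7 repeats 783 with the same duration. Section 13.7 adds one adjustment: if at most 10% of patients have failed to reach surgery once 400 are enrolled, accrual stops at 700.

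**Screening.** Section 13.6 puts smoking prevalence at 42%, expects 90% of those smokers to be motivated and enrol, rounds this to three screened per patient enrolled, and allows at most 20% to drop out before surgery. It concludes that the trial must screen "approximately 1878 oncology patients undergoing surgery to enroll 783 smoking patients". It then says that, allowing for refusal, "we would need to approach 2000 smoking oncology patients undergoing surgery to have 626 patients enroll in the study and undergo surgery".

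**Effect size.** Section 13.6 cites a large surgical database study in which "smokers undergoing non-cardiac surgery had an estimated 40% increased odds of developing major morbidity and mortality within 30 days of surgery", and describes this as "over never smokers, representing a modest difference of between 10%-12% in the actual percentage of patients with major morbidity". After naming the primary comparison, it says: "We will hence power the study to detect a 10% difference in perioperative complication rates between the intervention and control groups". The design is 30% versus 20%, 313 per arm, two-sided 5% Fisher exact test, 80% power.

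**The concern.** The closing rule decides when the trial stops enrolling. Section 13.1.1 restricts the primary analysis population to randomized patients who had surgery, so the number operated is the sample size that the 80% power depends on. A rule that counts enrolments secures that number only while pre-surgical loss stays within the planned bound. The protocol can shorten enrolment when loss is low but has no way to lengthen it when loss is high.

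The screening count appears to multiply the wrong target by three, and the approach count is hard to square with the 90% enrolment rate a few lines above it. These affect recruitment planning, not inference.

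The 10–12 point figure is the only numerical effect difference that 13.6 reports before it sets a 10-point target. If it does not follow from the odds ratio beside it, the reader cannot tell what it measures.

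**Working it through.** **1. The plan's own sample size.** Inputs from 13.6: 30% versus 20%, two-sided 5%, 80% power. The continuity-corrected two-proportion formula gives 313 per arm (294 uncorrected). Exact enumeration of the two-sided Fisher test at 313 per arm gives power 80.2%. The 626 and the 80% reproduce.

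**2. Closing rules compared.** Operated = enrolled × (1 − loss before surgery).

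| Enrolled at closure | Loss | Operated | Fisher power, 30% vs 20% |
|---|---|---|---|
| 783 | 20% (planned maximum) | 783 × 0.80 = 626 | 80.2% |
| 700 | 10% (limit for the early stop) | 700 × 0.90 = 630 | about 80% |
| 783 | 25% (assumed) | 783 × 0.75 = 587 | about 78% (77.6% at 294 per arm) |
| 783 | 30% (assumed) | 783 × 0.70 = 548 | about 74% (274 per arm) |

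The 25% and 30% rows are assumptions beyond the plan's stated bound. Under the rule in 1.3 and 1.4, 626 operated would need 626/0.75 = 835 or 626/0.70 = 895 enrolled.

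The shared duration does not settle which rule is meant. At 150 evaluable patients a year, 626/150 = 4.17 years, or about 4 years 2 months. That is the time to reach 626 evaluable patients. Section 13.7 attaches it to 783 enrolled, which fits only at 20% loss.

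**3. Screening.** The fraction screened who enrol is 0.42 × 0.90 = 0.378, or one in 2.65.

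- To enrol 783: 783/0.378 = 2071; at the rounded three to one, 3 × 783 = 2349.
- The stated 1878 is 3 × 626, so the ratio was applied to patients operated rather than patients enrolled.
- At 0.378, screening 1878 would enrol 1878 × 0.378 = 710, not 783.
- If the 2000 approached were all surgical patients, 2000 × 0.378 = 756 would enrol. If they were all smokers, as the text says, the count does not fit 90% enrolment unless a further refusal rate applies, and none is given.

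**4. Odds ratio and risk difference.** For an unadjusted odds ratio OR and reference risk p, the risk difference is p·OR/(1 − p + p·OR) − p. Its maximum over all p is (√OR − 1)/(√OR + 1). With OR = 1.4, √1.4 = 1.1832, so the maximum is 0.1832/2.1832 = 8.4 points, reached at 45.8% versus 54.2%. The smallest odds ratio that can give a difference d is [(1 + d)/(1 − d)]²: (1.10/0.90)² = 1.49 for 10 points and (1.12/0.88)² = 1.62 for 12 points.

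**The case against.** **On accrual:** 13.6 plans for at most 20% loss, and within that bound 783 enrolled always gives at least 626 operated; the early stop at 700 is also sound at 10%. This stands. A reader might infer that the 783 rule leaves the trial underpowered. The documents do not support that: the shortfall arises only if loss exceeds the plan's own limit, and it costs roughly 2 to 6 points of power over the assumed range. What remains is that the two rules differ and that nothing covers a loss above 20%.

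**On the approach count:** the sentence is conditional on refusal, which implies a further loss of unstated size. A reader might divide 783 by 0.90 and put that forward as the right number of smokers to approach. That sets aside the condition, so the text can be called unclear but not replaced by that figure.

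**On the odds ratio:** the 10–12 points summarises a cited study that is not available here. The 40% may be an adjusted odds ratio and the difference crude, in which case the crude difference can exceed 8.4 points. The outcomes are also worded differently: listed perioperative complications for the 25–30% rate, major morbidity and mortality within 30 days for the odds, major morbidity for the difference. This also stands. It rules out asserting a corrected value, such as the 6 to 7.5 points obtained by applying 1.4 to 25–30%. Even so, a crude difference is not what the odds ratio represents, so the sentence needs attention on either reading.

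A reader might go further and conclude that the true effect is smaller than 10 points and the power well under 80%. That does not follow. The smoker versus never-smoker contrast is observational and is not a varenicline versus placebo difference, and the link to the target through the word hence is only contextual. Section 1.1.2 also reports a 41% relative reduction from stopping smoking, which 13.6 does not cite and which does not compare arms either.

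**Conclusion.** The point holds in three parts, in order of consequence.

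- **Closing rule:** the contradiction is plain in the text. It has no effect on power at a loss of 20% or less; at an assumed 25–30% loss, closing at 783 gives about 587–548 operated and about 78–74% power for 30% versus 20%.
- **Screening count:** 1878 is wrong by the plan's own inputs, which give about 2071, or 2349 at three to one. The 2000 approached is ambiguous rather than shown to be wrong.
- **Odds ratio:** 40% higher odds cannot represent 10–12 points if it is an unadjusted odds ratio for the same outcome, since the ceiling is 8.4. Whether that condition holds cannot be decided without the cited source.

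The closing-rule and screening findings are firm. On the third, the ceiling is exact, but whether the 10–12 points is itself wrong remains open. The design calculation, test and endpoint are unaffected.

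**What to change.** 1. State one closing rule in 1.3, 1.4, 13.6 and 13.7. Closing at 626 operated protects the stated 80% power; the small downside is that enrolment could exceed 783. If a fixed enrolment is preferred, say so in 1.3 and 1.4 and state what happens if more than 20% miss surgery.
2. In 13.6, replace 1878 with about 2071, or 2349 if three to one is kept. State whether the 2000 approached are smokers or all surgical patients, and what refusal rate is assumed.
3. In 13.6, check the 10–12% against the cited study. Either correct it from that source or say that it is a crude difference that does not follow from the odds ratio. Do not insert a recalculated figure without the source.

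Keep 626 patients and 80% power for 30% versus 20%. The cost is one source check, a few sentences in 13.6, and one decision on the closing rule carried through four sections.

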13.7 Accrual rate and study duration

From accrual estimates provided by sites in this survey, we anticipate accruing 150 evaluable patients per year. Multiple surveys have been conducted to obtain realistic accrual expectations as well as detailed descriptions as to how patients will be accrued, treated, and assessed at each site. This study accrual will close when 783 study patients have been enrolled; therefore, we anticipate patient accrual to be completed in approximately 4 years and 2 months. If, after 400 patients have been enrolled to the study, the proportion of patients who fail to undergo surgery is $\leq 10\%$; then accrual to the study will be stopped when 700 patients have been enrolled, as this would produce the required 626 patients for the primary analysis.

13.8 Monitoring

This study will be monitored by the Alliance Data and Safety Monitoring Board (DSMB), an NCI-approved functioning body. Reports containing efficacy, adverse event, and administrative information will be provided to the DSMB every six months as per NCI guidelines.

This study will be monitored by the Clinical Data Update System (CDUS) version 2.0. An abbreviated report containing cumulative CDUS data will be submitted quarterly to CTEP by electronic means. Reports are due January 31, April 30, July 31, and October 31.

13.9 Adverse Event Stopping Rule

The stopping rule specified below is based on the knowledge available at study development. We note that the Adverse Event Stopping Rule may be adjusted in the event of either (1) the study re-opening to accrual or (2) at any time during the conduct of the trial and in consideration of newly acquired information regarding the adverse event profile of the treatment(s) under investigation. The study team may choose to suspend accrual because of unexpected adverse event profiles that have not crossed the specified rule below. CTCAE v4.0 will be used to determine grading for these stopping rules.

Accrual will be temporarily suspended to this study if at any time we observe events considered at least possibly related to study treatment (varenicline) (i.e., an adverse event with attribute specified as “possible”, “probable”, or “definite”) that satisfies the following:

- If 3 or more patients in the first 15 treated patients or, if at any time after the first 15 patients are enrolled, 20% or more patients develop \geq grade 4 non-hematologic adverse events felt to be at least possibly related to treatment, the study team will review the data to determine the proper course of action. These actions may include further adverse event monitoring, suspension of accrual, dose modification, or closure of the trial.

We note that we will review grade 4 and 5 adverse events deemed “unrelated” or “unlikely to be related”, to verify their attribution and to monitor the emergence of a previously unrecognized treatment-related adverse event.

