4.6 Treatment Assignments and Blinding

Patients will be randomized 1:1 to receive one of two blinded treatments:

Intervention Group: Participants will receive varenicline for 12 weeks plus a brief no-smoking message from the surgical team and behavioral support provided by a telephone smoking quitline (NCI's [name]).

Control Group: Participants will receive placebo for 12 weeks plus a brief no-smoking message from the surgical team and behavioral support provided by a telephone smoking quitline (NCI's [name]).

After the treatment assignment has been ascertained in the OPEN application, the patient's study medication code number will be displayed on the confirmation of registration screen.

The pharmacist or designated contact person at the treating site will maintain records that indicate the identity of the patient and their corresponding study medication code number.

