13.0 STATISTICAL CONSIDERATIONS

13.1 Study Design

This is a randomized, double-blind, placebo-controlled, phase III trial evaluating varenicline vs. placebo for reduction in post-surgical complications through 24 weeks after surgery in lung cancer patients who undergo surgery and are motivated to stop smoking. A parallel group design will be utilized for this two-arm study: varenicline vs. placebo. Both arms will also include a brief no smoking message from the surgical team and the NCI Quitline.

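### The adverse-event rule in Section 13.9 names no arm; read literally it pools varenicline with placebo, and a 20% event rate on varenicline would then trigger it in only about 24% to 40% of trials.

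*Combined protocol and SAP*

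**What the plan says.** Section 13.9 of the combined protocol and SAP opens its rule with "Accrual will be temporarily suspended to this study if at any time" qualifying events are seen. It describes those as "events considered at least possibly related to study treatment (varenicline"), meaning an attribution of possible, probable or definite. The rule has two limbs. The first is "If 3 or more patients in the first 15 treated patients". The second is "if at any time after the first 15 patients are enrolled, 20% or more patients develop" such an event. Both concern non-hematologic events of grade 4 or higher.

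Neither limb names an arm, an unblinded count or a comparison with placebo. When the rule is met, the study team reviews the data, and the section adds: "These actions may include further adverse event monitoring, suspension of accrual, dose modification, or closure of the trial".

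Section 4.6 states: "Patients will be randomized 1:1 to receive one of two blinded treatments". Section 13.1 confirms the double-blind, placebo-controlled design. Section 10.1 says that bottles are labelled so that local investigators do not know their contents. Section 13.8 provides periodic review: "Reports containing efficacy, adverse event, and administrative information will be provided to the DSMB every six months". It does not say whether adverse events are shown by arm.

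**The concern.** The limits of 3 in 15 and 20% are of the kind used when every counted patient receives the drug. Here about half of the counted patients receive placebo. The attribution wording cannot remove them, because the investigator who attributes the event does not know the assignment. If severe related events are rare on placebo, the pooled percentage is roughly half the percentage on varenicline, and the rule stays silent at rates that its own limit appears meant to catch.

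At stake is the one numeric safety trigger in the plan. The primary efficacy analysis is not affected.

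A second, smaller matter sits in the same section. The lead-in says that accrual is suspended when the rule is met, while the bullet lists suspension as one of several actions that may follow review.

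**Working it through.** **Inputs from the documents.** First limb: 3 or more of 15 (13.9). Continuing limb: 20% or more after the first 15 (13.9). Allocation: 1:1 (4.6). Maximum enrolment: 783 (13.7).

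**Input not in the documents.** The placebo rate of severe events judged possibly related. It is assumed to lie between 0% and 5%.

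**The plan's own figure.** 3/15 = 0.20, so the two limbs agree at 20%. The plan gives no trigger probabilities, so there is nothing further to reproduce.

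**Pooled rate.** With 1:1 allocation, p(pooled) = [p(varenicline) + p(placebo)] / 2.
- Varenicline 20%, placebo 0%: (0.20 + 0)/2 = 0.10.
- Varenicline 20%, placebo 5%: (0.20 + 0.05)/2 = 0.125.
- For the pooled rate to be 20%, varenicline must be at 0.40 − p(placebo): 40% with placebo at 0%, 35% with placebo at 5%.

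**First limb.** P(X ≥ 3), with X binomial (15, p):
- p = 0.10: 18.4%. With fixed splits of 7 or 8 varenicline patients among the 15: 14.8% or 20.3%.
- p = 0.125: 28.7%.
- p = 0.20 (all 15 on varenicline): 60.2%.

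**Both limbs.** Exact binomial recursion, one patient at a time. It stops at 3 events within the first 15, or afterwards as soon as events/patients ≥ 0.20.

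| Count | True rates (varenicline / placebo) | Met by 15 | Ever met |
|---|---|---|---|
| Pooled, to 783 | 20% / 0% | 18.4% | 23.9% |
| Pooled, to 783 | 20% / 1% | 20.4% | 26.8% |
| Pooled, to 783 | 20% / 2% | 22.4% | 29.8% |
| Pooled, to 783 | 20% / 5% | 28.7% | 39.7% |
| Pooled, to 783 | 30% / 0% | 39.6% | 58.3% |
| Varenicline only, to 392 | 20% / any | 60.2% | 93.1% |

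The figure 392 is half of 783, rounded up. Counted on varenicline only, the cumulative probability is already 80% by 50 varenicline patients and 90% by 200.

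**Later looks.** With rates of 20% and 0%, the chance that the pooled proportion is at or above 20% is 2.5% at 50 patients and 0.2% at 100. The pooled rule, if it fires at all, fires early.

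**Break-even.** The pooled rule is ever met in half of trials at a pooled rate of about 13.9%. That needs a placebo rate near 2 × 13.9% − 20% = 7.8%.

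**False triggers at the first look.**
- True rate 5% in both arms: pooled 3.6%; varenicline only, also 3.6%, since 15 patients are counted at the same rate; limits applied to each arm separately, 1 − (1 − 0.0362)² = 7.1%.
- Varenicline 10%, placebo 0%: pooled rate 5%, so 3.6% pooled; varenicline only 18.4%.

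All figures assume independent events, and the ever-met figures also assume reporting without delay and a check after every patient. Less frequent checks would lower the ever-met figures.

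**The case against.** **Pooling is inferred.** Section 13.9 does not say that the arms are combined, and treatment assignments must be available centrally, because interim comparisons of the primary endpoint accompany the DSMB reports (13.10). A by-arm count is therefore possible. This stands as a limit on the claim: what can be shown is that the denominator is unspecified and that the literal reading is pooled. No section supplies a by-arm count, and the review is given to the study team.

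**Other safeguards exist.** Section 8.2.4 stops study drug after any grade 4 event. Section 9.3 requires 24-hour notice of grade 4 and 5 serious events. Section 13.9 lets the team suspend accrual below the limit, revise the rule, and check severe events called unrelated. The DSMB sees reports every six months. All of this stands and limits the consequence, but none of it carries a numeric by-arm trigger.

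**The scenario is remote.** The safety data summarised in Section 10.1 do not suggest 20% severe related events. That is fair, but 20% is the rule's own limit, and it is at that limit that the rule should be judged.

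**Stronger readings.** A reader might infer that the rule has half its intended sensitivity. The documents state no intended sensitivity; what halves, with no placebo events, is the event rate. A reader might also infer that the rule would usually miss a 30% rate, from the 40% chance at the first 15. With the continuing limb the pooled rule is ever met in 58% of trials at that rate.

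**Suspension and review can be read together**, as a temporary hold followed by a decision. That is possible, but the text does not say so.

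**Conclusion.** The concern holds as a defect in specification with a measurable effect. On the literal pooled reading, a true varenicline rate equal to the 20% limit meets the rule in 18% to 29% of trials by the first 15 patients and in 24% to 40% at any time, for an assumed placebo rate of 0% to 5%. Counted on varenicline patients only, the figures are 60% and about 93%. A pooled 20% corresponds to 35% to 40% on varenicline.

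The statement that the rule would usually not trigger rests on the placebo rate and would fail above about 8%. The documents do not support saying that pooling was intended, or that patients are otherwise unmonitored. The change is worth making because it is cheap and concerns the only numeric safety trigger.

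**What to change.** In Section 13.9:

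1. Keep the stated limits and say that the denominator, in both limbs, is varenicline-treated patients. This also removes the shift from treated patients in the first limb to enrolled patients in the second.
2. Have the unblinded statistician who prepares the DSMB reports apply the count to that arm, with the placebo count shown beside it. The blinded study team is told only that the rule was met.
3. Reconcile the lead-in on suspension with the bullet that lists suspension as a possible action, so that one consequence is stated. Which one is for the sponsor to decide.

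**Cost.** A wording change and a by-arm tabulation. Fifteen varenicline patients means about 30 enrolled, so the first look completes later; the existing pooled 3-of-15 check can be kept alongside to cover that gap. False triggers rise whenever the varenicline rate exceeds the placebo rate, and also if the pooled check is kept as a second trigger. Applying the limits to both arms separately would roughly double them at the first look (3.6% to 7.1% at a true 5% rate) and would let the placebo arm trip a rule about varenicline, so a varenicline-only count is preferable.
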